There are two aims. **Aim 1 (formative stage)** involves developing an online provider intervention for HIV care providers to gain knowledge and skills to address the impact of experiencing intersectional stigma and discrimination, with a particular focus on medical mistrust, using input from key community stakeholders. We have been engaging community stakeholders via UCLA CHIPTS CAB to provide feedback on the intervention content. Based on CAB's suggestion, we conducted interviews with 21 HIV care consumers to inform the development of this intervention. In addition, we have conducted a usability test in two online groups of HIV care providers ( $n = 18$ ) to pilot test the intervention protocol. We have conducted qualitative feedback interviews with the pilot usability test participants to elicit feedback and revise the intervention protocol accordingly. **Aim 2 (pilot RCT)** involves conducting a pilot randomized controlled trial (RCT) in 60 providers caring for patients/clients at risk or living with HIV to test the intervention ( $n = 30$ ) against a no-treatment control group ( $n = 30$ ). Similar to the usability test, the intervention will be delivered by trainers from CAPTC (including a recorded session and a live training session via Zoom). Provider training outcomes will include providers' use of skills learned in the intervention to address intersectional stigma and medical mistrust using hypothetical patient scenarios, and provider-reported HIV service delivery outcomes. Outcomes will be assessed at baseline, immediately post-intervention, and at 6-month follow-up. A mixed-method process evaluation will be conducted at post-intervention to assess the acceptability, feasibility, and appropriateness of the online intervention.

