## Statistical Analytic Plan

Consistent with R34 guidelines, our primary purpose is to collect preliminary data and exploratory analyses on feasibility, acceptability, and outcomes, to calculate effect size estimates to assist planning for a fully powered RCT. Hence, we do not expect to have sufficient statistical power to adequately examine effects, and conducting formal tests for measures of effect size is not justified with limited sample size. Multilevel modeling will be used to account for multiple observations nested within providers. The intervention effect of interest will be a significant interaction between intervention condition (intervention vs. control) by time (pre, post, 6-month follow-up) on outcome variables. We hypothesize that participants in the intervention condition, compared to those in the control condition, will show greater increases in the number of empathic responses to medical mistrust, perceived importance, and the number of strategies (e.g., validation, MI-consistent statements, behavioral change techniques) used during simulated role-play, and perceived importance from pre to post and 6-month follow-up; intervention participants will also show a greater reduction in the percentage of patients lost to care, a greater increase in the percentage of patients virologically suppressed, and a greater increase in the percentage of patients who initiated PrEP, relative to control participants, from pre to post and 6-month follow-up. Analyses will use the standard intent-to-treat approach, in which we will analyze participants as belonging to the intervention condition they were randomized to, regardless of later non-response or loss at follow-up. The multilevel modeling approach uses a full information maximum likelihood estimator, meaning that all information is included in the analysis under the assumption that the data are missing at random or missing completely at random. For the quantitative process evaluation measures (i.e., AIM, IAM, FIM), we will report the descriptive statistics (e.g., mean, standard deviation, and range).

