## Protocol Amendment

The study protocol was last reviewed by the study Data Safety and Monitoring Board (DSMB) in April 2023, prior to recruiting the first participant. Since then, there have been several changes to the protocol. Initially, we planned to conduct post-assessments approximately 4-6 weeks following the baseline for control participants. However, scheduling training participants proved to be time-consuming (particularly during the summer), resulting in the interval between the baseline and immediate post-assessment extending to approximately 2-3 months. Consequently, control participants were also assessed 2-3 months following their baseline assessment. Secondly, the study team decided to eliminate the collection of role-play assessments at 6 months due to several considerations: 1) the primary interest and timeframe for the primary outcomes are changes from pre to post, 2) the response rate for role-play was low at post-assessment (see Table 2), 3) the participant burden was high compared to surveys, 4) conducting role-play assessments was time-consuming for the study team, necessitating a reallocation of resources to focus on pre-to-post changes, and 5) the surveys collected from baseline to 6-month follow-up include open questions on helpful responses to mistrust in hypothetical patient scenarios, which serve as proxies for provider responses in role play simulations. Thirdly, we increased the incentives for completing the survey and the brief role-play assessment at post-assessment or follow-up. Previously, we offered \$50 for completing both the survey and the assessment with a study coordinator or research assistant. However, participants in the control group received no training and had limited contact with the study team after the baseline assessment was completed (in contrast, the training group received numerous scheduling calls and completed training, including a 2-hour live session). We observed a relatively low response rate for the post-assessment in the control group. Therefore, we increased the incentives to \$50 for completing the survey and an additional \$50 for the assessment. This amendment was approved by RAND's Human Subject Protection Committee (RAND's IRB) in November 2023.

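### For outcomes analysed with a linear mixed model, maximum likelihood in about 60 providers makes standard errors some 2–3% too small; REML with Kenward-Roger degrees of freedom is a cheap refinement, at the price of wider intervals.

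*Combined protocol and SAP*

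**What the plan says.** The Statistical Analytic Plan sets the model ("Multilevel modeling will be used to account for multiple observations nested within providers") and the estimator ("The multilevel modeling approach uses a full information maximum likelihood estimator"). The choice of estimator is justified by its use of every available observation, with missingness taken to be at random or completely at random. The target is stated as "The intervention effect of interest will be a significant interaction between intervention condition (intervention vs. control) by time (pre, post, 6-month follow-up". No outcome distribution, covariance structure, reference distribution or degrees-of-freedom method is named.

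The Abstract describes "conducting a pilot randomized controlled trial (RCT) in 60 providers", 30 per arm. The Protocol Amendment section drops the 6-month role-play, so that primary outcome has two time points. Among its reasons it states that "the response rate for role-play was low at post-assessment (see Table 2". It also reports relatively low post response among controls. The text available for review gives no response figures. Under Assessment Procedures, both primary outcomes are defined as counts of coded statements or techniques.

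**The concern.** ML estimates variances as if the fixed effects were known. With a few dozen providers this biases the variances, and so the standard errors, downwards. Reading the result against a normal rather than a t distribution adds a second error in the same direction. Both grow as the number of providers with post data falls, and the role-play outcome is the one with two time points and documented low response.

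The pilot exists to supply effect size estimates for planning a larger trial, and the SAP words its effect of interest as a significant interaction. A standard error that is systematically too small overstates the precision of those estimates and makes a significant interaction slightly too easy to obtain. REML is also likelihood-based and uses all observations under missing at random, so the SAP's reason for choosing its estimator is kept.

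**Working it through.** The plan has no figure of its own to reproduce: it gives no alpha, effect, standard deviation, power or interval width. The 30 + 30 = 60 adds up.

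**Inputs.** From the documents: 60 providers, 30 per arm; ML; pre-to-post as the primary contrast. Assumed: two-sided 95% intervals; 20 to 60 complete pairs, equally split; normal outcome; within-provider correlation 0.5 in the simulations (0.3 and 0.7 also tried).

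**Closed form.** Take the difference between arms in pre-to-post change, N complete pairs, pooled variance. ML divides the sum of squares by N, REML by N − 2. Then:

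- standard error ratio ML/REML = √((N − 2)/N)
- coverage, ML with normal quantile = P(|t| < 1.96 × √((N − 2)/N)) on N − 2 degrees of freedom
- width, REML with t relative to ML with normal = t(0.975; N − 2) / (1.96 × √((N − 2)/N))

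For N = 60: √(58/60) = 0.983; 1.96 × 0.983 = 1.927; P(|t| < 1.927) on 58 df = 94.1%; 2.002/1.927 = 1.039.

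| N pairs | ML SE too small by | ML + normal | ML + t | REML + normal | REML + t | Interval wider by |
|---|---|---|---|---|---|---|
| 60 | 1.7% | 94.1% | 94.6% | 94.5% | 95% | 3.9% |
| 40 | 2.5% | 93.6% | 94.4% | 94.3% | 95% | 6.0% |
| 30 | 3.4% | 93.1% | 94.2% | 94.0% | 95% | 8.2% |
| 20 | 5.1% | 92.1% | 93.8% | 93.4% | 95% | 13.0% |

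At 40 pairs, ML with a normal quantile loses 1.4 points of coverage. With a t quantile it still loses 0.6. So a little under half of the loss belongs to the estimator the SAP names, and the rest to a quantile it does not name.

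**Simulation.** Random-intercept model with condition, time and interaction; 60 providers; two visits; missing at random; 3,000 runs per setting (Monte Carlo standard error of coverage 0.4 points). REML used t quantiles with within-provider degrees of freedom.

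| Post response, control/intervention (assumed) | SE ratio ML/REML | ML + normal | REML + t | Interval wider by |
|---|---|---|---|---|
| 100%/100% | 0.983 | 93.9% | 94.9% | 4% |
| 70%/90% | 0.980 | 93.5% | 94.6% | 5% |
| 50%/80% | 0.976 | 93.7% | 94.9% | 6% |
| 40%/60% | 0.972 | 93.8% | 95.4% | 8% |
| 30%/40% | 0.964 | 91.5% | 94.2% | 11% |

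With three visits, in the first four response settings, ML with normal quantiles covers 93.5–94.3% and REML with t 94.7–95.2%. At 50%/80% response, two visits and correlation 0.3 or 0.7, the figures are 93.4–93.5% and 94.6–94.8%.

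**Effect on the interaction test.** Changing from ML with normal to REML with t, the chance of significance at an assumed effect of 0.5 SD of change falls from 50.7% to 47.8% (N = 60), 37.9% to 33.8% (N = 40) and 31.2% to 26.2% (N = 30). Part of this is removal of excess type I error, which under ML with normal quantiles is 5.9%, 6.4% and 6.9%.

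**Where the change does not help.** With non-random dropout (50%/80% response, true effect 0.50) the mean estimate is 0.23, and coverage is 85.5% under ML and 87.9% under REML with t. For overdispersed counts analysed linearly (assumed mean 3), REML with t covers 94–96% at full response or with the lower response in controls. In a stress case with the lower response in the higher-mean intervention arm, the reverse of what the amendment reports, it covers 86.6% (ML 84.1%).

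**The case against.** The strongest reply is that this is largely a preference between estimators, with a 2–3% effect on standard errors, in a pilot that disclaims formal testing. The point estimate hardly moves. That stands, and it limits the point to an optional improvement.

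The SAP also states no interval, quantile or degrees-of-freedom method, so the coverage of 93–94% describes one possible software default. That stands too. With t quantiles and ML variances the shortfall is under one point for 30 to 60 pairs. The silence is itself a reason to name a method.

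The primary outcomes are counts. If they are fitted with a Poisson or negative binomial mixed model, standard REML with Kenward-Roger does not directly apply. This also stands, and the wording of the fix reflects it.

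A reader might infer that the change costs nothing. It does not come free: intervals widen, significance becomes somewhat less likely, and REML likelihood-ratio tests cannot compare models with different fixed effects, including the condition-by-time terms. Kenward-Roger F tests take their place.

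A reader might also infer that REML deals with the low post response. It only adjusts for the smaller number of observations. Selective non-response among controls is a larger and separate threat, and the change leaves it almost untouched.

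**Conclusion.** The point holds in a limited form. For outcomes analysed with a linear mixed model, the named estimator makes standard errors about 2–3% too small (1.7% at 60 complete pairs, 3.4% at 30). With normal quantiles, nominal 95% intervals cover about 93–94%, and about 92% only if response is very low. REML with small-sample degrees of freedom brings coverage to about 95% for a roughly normal outcome under missing at random.

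This rests on assumed response rates, correlation and quantiles. The simulations used within-provider degrees of freedom, not Kenward-Roger itself; the two agree for complete pairs, and Kenward-Roger was not run separately for unequal response.

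It would go too far to say that the SAP's intervals are wrong as written, since it specifies none, or that the interval is the pilot's main output. The stated purpose is preliminary data on feasibility, acceptability and outcomes, and effect size estimates for planning.

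**What to change.** Replace the estimator sentence in the Statistical Analytic Plan with:

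> Outcomes analysed with linear mixed models are fitted by restricted maximum likelihood using all available observations under missing at random, with Kenward-Roger degrees of freedom for intervals and for the condition-by-time test; if a count outcome is instead analysed with a Poisson or negative binomial mixed model, that model is named and this sentence does not apply.

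This needs a software option and no new data. The price is intervals about 4–8% wider for 60 down to 30 complete pairs (11–13% in the lowest-response settings tried), a chance of a significant interaction lower by about 3–5 points at 0.5 SD, and no REML likelihood-ratio tests of fixed effects. Non-random control-arm non-response needs its own sensitivity analysis.

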## Protocol Amendment

The study protocol was last reviewed by the study Data Safety and Monitoring Board (DSMB) in April 2023, prior to recruiting the first participant. Since then, there have been several changes to the protocol. Initially, we planned to conduct post-assessments approximately 4-6 weeks following the baseline for control participants. However, scheduling training participants proved to be time-consuming (particularly during the summer), resulting in the interval between the baseline and immediate post-assessment extending to approximately 2-3 months. Consequently, control participants were also assessed 2-3 months following their baseline assessment. Secondly, the study team decided to eliminate the collection of role-play assessments at 6 months due to several considerations: 1) the primary interest and timeframe for the primary outcomes are changes from pre to post, 2) the response rate for role-play was low at post-assessment (see Table 2), 3) the participant burden was high compared to surveys, 4) conducting role-play assessments was time-consuming for the study team, necessitating a reallocation of resources to focus on pre-to-post changes, and 5) the surveys collected from baseline to 6-month follow-up include open questions on helpful responses to mistrust in hypothetical patient scenarios, which serve as proxies for provider responses in role play simulations. Thirdly, we increased the incentives for completing the survey and the brief role-play assessment at post-assessment or follow-up. Previously, we offered \$50 for completing both the survey and the assessment with a study coordinator or research assistant. However, participants in the control group received no training and had limited contact with the study team after the baseline assessment was completed (in contrast, the training group received numerous scheduling calls and completed training, including a 2-hour live session). We observed a relatively low response rate for the post-assessment in the control group. Therefore, we increased the incentives to \$50 for completing the survey and an additional \$50 for the assessment. This amendment was approved by RAND's Human Subject Protection Committee (RAND's IRB) in November 2023.

## Appendix. Description of the Provider Intervention

Modules: Goals	Core Components	Examples of Teaching Points

1. Background (45 min): to gain knowledge about intersectional stigma, discrimination, medical mistrust, and their impact on adherence, care engagement, and health outcomes
	
a) Intersectional stigma and discrimination, including various types of stigma common in Black and Latinx individuals living with HIV (e.g., HIV infection, mental illnesses, drug/alcohol use, sexual minorities, racial/ethnic minorities, immigration status)
 
b) Medical mistrust as a result of intersectional stigma and discrimination, including the history/development of medical mistrust and the function of medical mistrust (e.g., survival mechanism)
 
c) The negative impact of intersectional stigma and medical mistrust on treatment adherence, care engagement, and health outcomes
 
d) Benefits of understanding and acknowledging intersectional stigma and medical mistrust
	
 
- Intersectional stigma is linked to multiple discrimination
 
- Medical mistrust stems from knowledge of current and historical injustices in healthcare and U.S. society in general due to having one or multiple stigmatized identities
 
- Mistrust can be a form of resilience; it is not necessarily harmful and can be viewed as an understandable and adaptive survival mechanism
 
- HIV treatment nonadherence can be related to hearing HIV-related mistrust beliefs from social network members
 
- Medical mistrust can negatively affect HIV prevention outcomes (e.g., condom use) and treatment outcomes (adherence to ART, detectable viral load)
 
- Understand medical mistrust as a set of assumptions/beliefs that may affect patient's thoughts, feeling, and behavior during a specific healthcare visit or a conversation about starting a new treatment
 


2. Skill training (2-hour live session):
 
2a. Validation/Affirmation (0.75 hr): to be able to acknowledge and validate the patient's experience of discrimination due to intersectional stigma and expression of medical mistrust
	
a) Empathy, reflective listening
 
b) Acknowledge the historical and current context of intersectional stigma and discrimination as a root cause of medical mistrust
 
c) Validate the negative feelings toward healthcare or authorities as well as their concerns that stem from medical mistrust
	
 
- In response to the expression of mistrust: "Communities who were mistreated and discriminated against often distrust the healthcare system or their doctors. This makes sense that people would want to put their guard up to protect themselves from discrimination. This may explain why some believe that the government or health care system cannot be trusted and maybe withholding treatment of HIV for Black people."
 
- "If there is anything that I do/say, or someone at the clinic do/say, that makes you feel uncomfortable, would you let me know?"
 


2b. Motivational interviewing in health care and behavior change techniques (1.25 hrs): to be able to use communication strategies/styles that are consistent with motivational interviewing and that promote behavior change to address any ambivalence or resistance related to adherence, treatment recommendations, and care engagement in a sensitive manner to promote better clinical outcomes
	
a) Being able to identify ambivalence in patients that is related to medical mistrust
 
b) Using a non-judgmental and non-confrontational stand, rolling with resistance
 
c) Leaving room for the patient to bring up concerns or probe for mistrust-related concerns
 
d) Asking short, open-ended questions
 
e) Using listening skills (e.g., reflecting)
 
f) Asking for permission to share information, offering choices and talk about what others do when informing
 
g) Provide accurate information about the treatment/condition and the medical advice/recommendations
	
 
- "What concerns you most about these medications? What are some reasons to not get or get [PrEP or other recommendation or treatment]?"
 
- "What do you already know about [HIV or other medication, recommendation, or treatment]? What would you most like to know about [HIV or other medication, recommendation, or treatment]"
 
- "What are some benefits for believing that [medication or treatment] is harmful or poisonous? What might be some downsides for believing this?"
 
- "Would it be alright if I shared something, and you can tell me what you think of this.... I understand there are many common assumptions and beliefs around [HIV or treatment]. A lot of them were natural responses to discrimination and mistreatment. At the same time, these doubtful feelings can deter people from getting effective treatment or coming to check-ups regularly."
 

3. Maintaining the progress (30 min): make action plans to maintain learning gains and increase chances of changing practice behaviors as a result of the intervention
	
a) Making action plans for maintaining the learning gains
	
 
- Discussing barriers and facilitators for implementing new skills
 
- Organizing learning collaboratives for providers to raise questions, and consult about experiences with patients (e.g., through an online chat room)
 

